10.3. Withdrawal From the Use of Research Samples

A subject who withdraws from the study will have the following options regarding the optional research samples:

- The collected samples will be retained and used in accordance with the subject's original separate informed consent for optional research samples.
- The subject may withdraw consent for optional research samples in which case the samples will be destroyed, and no further testing will take place. To initiate the sample destruction process, the investigator must notify the Sponsor study site contact of withdrawal of consent for the optional research samples and to request sample destruction. The Sponsor study site contact will, in turn, contact the substudy representative to execute sample destruction. If requested, the investigator will receive written confirmation from the Sponsor that the samples have been destroyed.

Withdrawal From the Optional Research Samples While Remaining in the Main Study

The subject may withdraw consent for optional research samples while remaining in the study. In such a case, the optional research samples will be destroyed. The sample destruction process will proceed as described above.

Withdrawal From the Use of Samples in Future Research

The subject may withdraw consent for use of samples for research (refer to Section 16.2.5). In that case, samples will be destroyed after they are no longer needed for the clinical study. Details of the sample retention for research are presented in the main ICF and in the separate ICF for optional research samples.

11. STATISTICAL METHODS

Statistical analysis will be done by the Sponsor or under the authority of the Sponsor. A general description of the statistical methods to be used to analyze the efficacy and safety data is outlined below. Specific details will be provided in the Statistical Analysis Plan (SAP). The SAP may be divided in three separate documents describing the analyses for the three study parts.

The statistical analyses in this study will be performed separately for each Study Part and will focus on the comparison of the two randomized treatment groups (ie, **2a**: guselkumab 100 mg q8w vs. **2b**: guselkumab 100 mg q16w) in Study Part 2. The analyses will be confirmatory for the primary endpoint, and exploratory for the major secondary endpoints and for all other secondary endpoints.

Descriptive statistics will include counts and proportions for categorical data, and mean, SD, median, interquartile range, and range for continuous data. Graphical data displays may also be used to summarize the data. The two-group large-sample normal approximation Wald Z-test with Mantel-Haenszel stratum weights for 'disease duration' will be used to compare the proportion of subjects responding to treatment. Continuous response parameters will be compared using an analysis of variance model with fixed effects for treatment group and disease duration and baseline value as a covariate. Time-to-event endpoints will be analyzed using Kaplan-Meier product limit methods to estimate the survival distributions and the median time-to-event. The confirmatory significance level for non-inferiority testing is fixed to a one-sided $\alpha=0.05$. Besides the confirmatory testing of the primary endpoint all other inferential statistical testing (including calculation of confidence intervals) are to be interpreted in the exploratory sense only.

11.1. Subject Information

Descriptive statistics by treatment group will be provided for subject dispositions, demographics, baseline disease characteristics, and prior and concomitant medications. Details will be provided in the SAP.

11.2. Sample Size Determination

This randomized, double-blind, parallel-group, multicenter phase 3b trial is designed to demonstrate that guselkumab 100 mg q16w treatment is non-inferior to guselkumab 100 mg q8w treatment in SRe as assessed by the proportion of subjects with an absolute PASI score <3 at week 68. A non-inferiority margin of 10% was chosen based on a minimally clinically meaningful difference. This margin was also used in CNTO1959PSO3009 (ECLIPSE) study and is therefore considered a valid approach for evaluating non-inferiority of a new treatment.

The null hypothesis H_0 and the alternative hypothesis H_A are formulated as follows:

- $H_0: P_T - P_S \leq -10\%$ ('inferiority')
- $H_1: P_T - P_S > -10\%$ ('non-inferiority')

where P_T and P_S denote the proportions of subjects with an absolute PASI score <3 at week 68 in the guselkumab 100 mg q16w treatment arm (P_T = proportion test treatment) and the guselkumab 100 mg q8w treatment arm (P_S = proportion standard treatment).

Based on data from CNTO1959PSO3002 the proportion of subjects with an absolute PASI score <3 at week 68 is assumed to be 90% for guselkumab 100 mg q8w. The expected difference in proportions between the treatment groups (guselkumab 100 mg q16w minus guselkumab 100 mg q8w) is 0%.

According to current international guidance documents ([CPMP, Points to consider on switching between superiority and non-inferiority 2001](#)) the intent-to-treat analysis set and the per-protocol analysis set should have equal importance in a non-inferiority trial and their use should lead to similar conclusions for a robust interpretation.

Therefore, the sample size estimation using the power approach is performed for the per-protocol analysis set as described below. No formal adjustment of the significance level is necessary ([CPMP, Points to Consider on Multiplicity Issues in Clinical Trials 2002](#)).

When the sample size in each group is 112, a two-group large-sample normal approximation Wald Z-test of proportions with a one-sided 0.05 significance level will have 80% power to reject the null hypothesis that the guselkumab 100 mg q16w treatment is inferior to the guselkumab 100 mg q8w treatment (the difference in proportions, $P_T - P_S$, is $\leq -10\%$) in favor of the alternative hypothesis that the guselkumab 100 mg q16w treatment is non-inferior to the guselkumab 100 mg q8w treatment (the difference in proportions is $> -10\%$), assuming that the expected difference in proportions is 0 and the proportion in the guselkumab 100 mg q8w treatment group is 90% (nQuery Advisor® 7.0).

Considering routine clinical conditions it is assumed that a rate of about 20% randomized subjects will not be evaluable for the per-protocol analysis in Study Part 2. Thus, 280 subjects (140 subjects per treatment group) are planned to be randomized in a ratio of 1:1 to meet the required sample size of 224 subjects (112 subjects per treatment group) for the per-protocol analysis.

Based on data from CNTO1959PSO3001 and CNTO1959PSO3002, it is anticipated that approximately 35% of enrolled subjects in Study Part 1 will be eligible for randomization at week 28 in Study Part 2. Thus, a total of 800 subjects should be enrolled in Study Part 1 to ensure that at least 280 subjects are eligible for randomization in Study Part 2. Accounting for a 10% drop-out rate of subjects ineligible for randomization at week 28 because of study discontinuation prior to week 28, it is therefore planned to enroll a total of 888 subjects in Study Part 1.

Note: Screenings and enrollments will be adjusted if necessary (without protocol amendment) to achieve 280 SRe at week 28. Ongoing subjects in Study Part I will continue to Part II if eligible, irrespective of whether or not 280 SRe are already randomized. Only screenings will be closed.

11.3. Efficacy Analyses

Analysis Data Set

The efficacy analyses will be performed separately for each Study Part. For all efficacy analyses to compare guselkumab 100 mg q16w vs. guselkumab 100 mg q8w in Study Part 2, all randomized subjects at week 28 will be included.

In Study Part 2 subjects will be analyzed according to the treatment group to which they were randomized regardless of the treatment they actually received (intent-to-treat analysis set).

The per-protocol analysis set will consist of all subjects in the intent-to-treat analysis set terminating the study without any major deviation of the protocol and its procedures. Subjects with major protocol deviations will be excluded from the per-protocol analysis.

The confirmatory analysis of the primary endpoint variable will be performed both for the intent-to-treat analysis set and the per-protocol analysis set.

In Study Part 1 and Study Part 3 all subjects treated with at least one dose of study drug will be included in the efficacy analyses. For all efficacy analyses in Study Part 1 and Study Part 3, subjects will be analyzed according to the treatment they actually received.

Primary Endpoint

The proportion of subjects with an absolute PASI score <3 at week 68 will be displayed in a frequency table providing the number and percentage of subjects. Graphical presentation will be presented by means of a bar chart.

To test the non-inferiority of guselkumab 100 mg q16w to guselkumab 100 mg q8w with a non-inferiority margin of 10% in Study Part 2, a one-sided ($\alpha=0.05$) two-group large-sample normal approximation Wald Z-test with Mantel-Haenszel stratum weights for 'disease duration' will be used. The Mantel-Haenszel estimate, the two-sided 90% Wald-type confidence limits, and the test for the difference of proportions will be computed by using Mantel-Haenszel stratum weights ([Mantel und Haenszel 1959](#)) and the Sato variance estimator ([Sato 1989](#)). Non-inferiority will be accomplished when the lower limit of the two-sided 90% confidence interval for the difference in response rates (guselkumab 100 mg q16w minus guselkumab 100 mg q8w) will be $> -10\%$ both for the intent-to-treat analysis and the per-protocol analysis.

Non-responder imputation will be applied for subjects with missing data for the primary endpoint as described in Section [11.11](#).

Major Secondary Endpoints

The major secondary endpoints will comprise the endpoints as defined in Section [2.1.2](#). Statistical analyses will be descriptive and exploratory only.

The proportion of subjects responding to treatment will be displayed in frequency tables providing the number and percentage of subjects. Graphical presentation will be presented by means of bar charts. In Study Part 2 the two-group large-sample normal approximation Wald Z-test with Mantel-Haenszel stratum weights for 'disease duration' will be used to compare the proportion of subjects responding to treatment. The Mantel-Haenszel estimate, the two-sided Wald-type 90% confidence limits, and the test for the difference of proportions in Study Part 2 will be computed by using Mantel-Haenszel stratum weights ([Mantel und Haenszel 1959](#)) and the Sato variance

estimator ([Sato 1989](#)). Exploratory statistical analyses of response parameters in Study Part 1 and Study Part 3 will be performed analogously, as appropriate.

Non-responder imputation will be applied for subjects with missing data for the major secondary endpoints as described in Section [11.11](#). Details will be provided in the SAP.

Other Secondary Endpoints

The other secondary endpoints will comprise the endpoints as defined in Section [2.1.2](#). Statistical analyses will be descriptive and exploratory only.

The proportion of subjects responding to treatment will be displayed in frequency tables providing the number and percentage of subjects. Graphical presentation will be presented by means of bar charts. For continuous response parameters absolute values and changes from baseline will be summarized by descriptive statistics and box and whisker plots.

In Study Part 2 the two-group large-sample normal approximation Wald Z-test with Mantel-Haenszel stratum weights for 'disease duration' will be used to compare the proportion of subjects responding to treatment. The Mantel-Haenszel estimate, the two-sided 90% Wald-type confidence limits, and the test for the difference of proportions in Study Part 2 will be computed by using Mantel-Haenszel stratum weights ([Mantel und Haenszel 1959](#)) and the Sato variance estimator ([Sato 1989](#)). Continuous response parameters in Study Part 2 will be compared using an analysis of variance model with fixed effects for treatment group and disease duration and baseline value as covariate. Time-to-event endpoints will be analyzed using Kaplan-Meier product limit methods to estimate the survival distributions and the median time-to-event. Exploratory statistical analyses of response parameters in Study Part 1 and Study Part 3 will be performed analogously, as appropriate. Details will be provided in the SAP.

Non-responder imputation (for binary endpoints) or Last Observation Carried Forward (LOCF) imputation (for continuous endpoints) will be applied for subjects with missing data for the other secondary endpoints as described in Section [11.11](#).

Criteria for Endpoints

Treatment failure: Subjects who discontinue study agent due to lack of efficacy, an AE, worsening of psoriasis, or who started a protocol-prohibited medication/therapy during the study period that could improve psoriasis are considered treatment failures. Treatment failure rules (TFR) will be applied after week 68 for a separate analysis. The treatment failure rules will be documented in detail in the SAP.

PASI 75 Responders:	Subjects with $\geq 75\%$ improvement in PASI from baseline at week 28
PASI 90 Responders:	Subjects with $\geq 90\%$ improvement in PASI from baseline at week 28
PASI 100 Responders	Subjects with 100% improvement in PASI from baseline at week 28
Maintenance of control of disease	Subjects with a PASI score < 3
Fluctuating disease:	absolute PASI score 3 to 5
Loss of disease control	absolute PASI score > 5

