- Proportion of subjects who achieve a PASI 75/90/100 response at weeks 20, 28, 68, 116, 164, and 220 per study group (**1, 2a, 2b, 2c, 3a, and 3b**)
- Time to loss of disease control (absolute PASI score > 5 at any visit) after treatment withdrawal beyond week 68 per study group (**3a and 3b**)
- Proportion of subjects with an absolute PASI score=0 at all of the following visits: weeks 12, 16, 20, and 28 (**study group 1**)
- Change from baseline (week 0) in Dermatology Life Quality Index (DLQI) score at weeks 28, 68, 116, 164, and 220 per study group (**1, 2a, 2b, 2c, 3a, 3b, and 3c**)
- Proportion of subjects who achieve a DLQI score 0/1 and < 5 at weeks 28, 68, 116, 164, and 220 per study group (**1, 2a, 2b, 2c, 3a, 3b, and 3c**)
- Change from baseline (week 0) in affected Body Surface Area (BSA) at weeks 12, 28, 52, 68, 80, 104, 116, 140, 164, 188, 212, and 220 (**all study groups**)
- Change from baseline (week 0) in the Nail Assessment in Psoriasis and Psoriatic Arthritis (NAPPA) score at weeks 28, 68, 116, 164, and 220 among subjects with nail psoriasis at baseline (week 0; **1, 2a, 2b, 2c, 3a, and 3b**)
- Change from baseline (week 0) in the signs and symptoms aggregate scores of the Psoriasis Symptoms and Signs Diary (PSSD) at weeks 28, 68, 116, 164, and 220 (**1, 2a, 2b, 2c, 3a and 3b**)
- Proportion of subjects who achieve a PSSD sign score=0 at week 68 among subjects with a PSSD sign score ≥ 1 at week 28 per study group (**2a, 2b, and 2c**)
- Association between trough serum guselkumab concentration and efficacy or serum biomarker level
- Association between trough serum guselkumab levels at weeks 20, 28, 36, and 68 and achieving a PASI score < 3 at week 68 per study group (**2a and 2b**)
- Proportion of subjects who were re-treated due to loss of disease control (PASI > 5) and regain control of disease (PASI < 3) 24 weeks after start of re-treatment (study groups **2d and 3c**)
- Safety and tolerability with regard to adverse events (AEs) and abnormal laboratory results (**all study groups**).

Refer to Section 9 for evaluations related to these endpoints.

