5. TREATMENT ALLOCATION AND BLINDING

Treatment Allocation/ Procedures for Randomization

Central randomization will be implemented in Study Part 2. Eligible subjects (confirmation by physician needed that the subject achieved a PASI score=0 at weeks 20 and 28) will be randomly assigned to one of two guselkumab treatment groups (ratio 1:1) based on a computer-generated randomization schedule prepared before the study by or under the supervision of the Sponsor. The randomization will be balanced by using randomly permuted blocks. The interactive web response system (IWRS) will assign a unique treatment code, which will dictate the treatment assignment and matching study drug kit for the subject. The requestor must use his or her own user

identification and personal identification number when contacting the IWRS and will then give the relevant subject details to uniquely identify the subject.

Subjects will be equally stratified in study group 2a and 2b during randomization for i) disease duration of ≤ 2 or >2 years (note: disease duration will be calculated from date at which first symptoms (plaque) were reported by subject to date of screening visit) and ii) for participation in substudy 1. Definitions when to stop/pause recruitment of subjects with longer disease duration will be provided in a separate document.

It is expected that about 280 of the subjects included in Study Part 1 will be categorized as SRe and thus be eligible for central randomization in Study Part 2. However, this number is not fixed but can be slightly exceeded if potential SRe are still in Part 1. To limit the number of subjects in Study Part 2 recruitment might be stopped before the limit of 900-1000 subjects in Study Part 1 has been reached but might also be extended if less than 280 subjects are likely to be defined as SRe.

Blinding

The investigator will not be provided with randomization codes. The codes will be maintained within the IWRS, which has the functionality to allow the investigator to break the blind for an individual subject.

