9.1.4. Study Part 2: Double-blind Treatment Phase

Subjects with a PASI score=0 at weeks 20 and 28 will be defined as SRe and are qualified for randomization in study group 2a or 2b. Following randomization via IWRS at week 28, eligible subjects will continue into the double-blind treatment period, with visits to be conducted every 8 weeks. The final study agent injection will take place at week 60, final assessments will be made at week 68.

Subjects starting a prohibited psoriasis treatment do have to complete a safety follow up visit at week 72 visit or 12 weeks after last dose of guselkumab, whichever comes first. It is expected that all visits in the double-blind treatment phase will occur within a range of ± 7 days. All study procedures and evaluations are to be conducted before administration of study drug. For further details on study agent administration, refer to Section 6.

Subjects not eligible for participation in the double-blind treatment period will continue to receive guselkumab 100 mg q8w until week 60 (last administration at week 60 visit) with final study assessments at week 68 and final safety follow-up visit at week 72.

All subjects who prematurely stop taking the study drug should complete the ETV and 12 weeks later the safety follow-up. For subjects who withdraw from study participation, every effort should be made to conduct final efficacy and safety evaluations.

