11.11. Handling of Missing Data

All available data will be included in the analyses and will be summarized as far as possible. If not otherwise specified, there will be no substitution of missing data, ie, missing data will not be replaced, missing data will be handled as 'missing' in the statistical evaluation ('observed cases analysis').

Non-responder imputation will be applied for subjects with missing data for the primary endpoint at week 68 as described below:

Subjects who do not maintain control of disease (absolute PASI score ≥ 3) or subjects who discontinue study treatment during the study before week 68 will be considered non-responders for the primary endpoint at week 68. In addition, subjects who do not return for evaluation at week 68 will be considered non-responders at week 68.

Non-responder imputation for the other binary endpoints will be performed analogously.

For continuous response parameters, the last available observation after baseline will be calculated and used for analysis in case of premature termination (Last Observation Carried Forward approach; LOCF).

LOCF may also be used as sensitivity analysis for binary response parameters. Treatment failure rules (TFR) will be applied after week 68 for a separate analysis. Additional sensitivity analyses may be done by applying different imputation rules for missing data (eg, 'multiple imputation'). An 'observed cases analysis' for all binary and continuous endpoints without substitution of missing data may also be used. A more detailed description of the handling of missing data will be provided in the SAP.

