5.5.1. Definition of Endpoint(s)

5.5.1.1. Psoriasis Area and Severity Index (PASI)

Efficacy endpoints related to the PASI score are defined below:

PASI 75 Responder

Subjects with $\geq 75\%$ improvement in PASI from baseline will be considered PASI 75 responders.

PASI 90 Responder

Subjects with $\geq 90\%$ improvement in PASI from baseline will be considered PASI 90 responders.

PASI 100 Responder

Subjects with a PASI score of 0 will be considered PASI 100 responders.

Time to loss of disease control

The time to loss of disease control is defined as time from the week 68 visit (start of withdrawal phase) to first date PASI is >5 within Study Part 3. In the absence of documented disease control, the time to loss of disease control will be censored at the date of the last PASI assessment until the week 116/164/220 visit. The time to loss of disease control will be computed as:

- Date of PASI >5 – Date of week 68, if the subject loses disease control,
- Date of last PASI assessment – Date of week 68, if the subject maintains disease control.
- In case the subject missed the week 68 visit, the start date of the withdrawal phase will be estimated as 8 weeks (56 days) after the week 60 visit.

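### Protocol 11.3 fixes PASI 75/90/100 response at week 28, which contradicts the multi-visit endpoint; read literally, the week 68 comparison says nothing about week 68 PASI

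*Protocol*

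**What the plan says.** The list of endpoint criteria in Protocol Section 11.3 gives the protocol's only definitions of PASI 75, 90 and 100 responders. All three end with the same visit; the PASI 100 entry is "Subjects with 100% improvement in PASI from baseline at week 28". The next three entries in that list (maintained control, fluctuating disease, loss of control) name no visit.

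Section 2.1.2 uses these responses in two ways. An other secondary endpoint is "Proportion of subjects who achieve a PASI 75/90/100 response at weeks 20, 28, 68, 116, 164, and 220 per study group". A major secondary endpoint is the time to PASI 75/90/100 response, by disease duration, in groups 1, 2a, 2b and 2c.

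Entry to the randomised comparison depends on week 28 status. Section 9.1.4 states "Subjects with a PASI score=0 at weeks 20 and 28 will be defined as SRe and are qualified for randomization", and Section 5 adds "confirmation by physician needed that the subject achieved a PASI score=0 at weeks 20 and 28".

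For missing data, Section 11.11 says of the primary endpoint that "subjects who discontinue study treatment during the study before week 68 will be considered non-responders for the primary endpoint at week 68" and that "subjects who do not return for evaluation at week 68 will be considered non-responders at week 68". It extends non-responder imputation by analogy to the other binary endpoints, and Section 11.3 also applies it to them.

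The Part 3 SAP, Section 5.5.1.1, defines the same responders with no visit; for PASI 100, "Subjects with a PASI score of 0 will be considered PASI 100 responders". It evaluates them at weeks 116, 164 and 220. Its Appendix 2 reports no important change from the protocol, and its itemised list does not mention this one.

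**The concern.** A status fixed at week 28 cannot serve an endpoint that is also read at weeks 20, 68, 116, 164 and 220, and it cannot yield a time to response. The conflict matters most at week 68. Subjects are randomised because they had PASI 0 at week 28, so the literal rule repeats the entry criterion when it should describe what happened under the two dosing intervals. In group 2c the error runs the other way: a subject with PASI above 0 at week 28 who clears by week 68 would not count as a PASI 100 responder.

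At stake is whether the q8w-q16w tables for PASI 75, 90 and 100 at week 68 carry any information on skin response. Section 11.3 asks for a between-arm test and a 90% confidence interval on these proportions. There is also a traceability problem, because the protocol and the Part 3 SAP define one endpoint in two ways and no reconciliation is recorded.

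**Working it through.** **1. The plan's own figures.** The documents give no figure for the PASI 75/90/100 comparison. The sample size belongs to the primary endpoint (PASI <3 at week 68) and reproduces: n per arm = (1.645 + 0.842)² × 2 × 0.90 × 0.10 / 0.10² = 111.3, rounded up to 112; power at 112 is 80.2%; 112 / (1 - 0.20) = 140 randomised per arm. No PASI 75/90/100 definition enters it.

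**2. The rule applied to single records.** The records are hypothetical. Improvement = (week 0 PASI - visit PASI) / week 0 PASI.

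| PASI at weeks 0/28/68 | Improvement at week 28 | Improvement at week 68 | Literal rule, read at week 68 | Visit-specific rule |
|---|---|---|---|---|
| Randomised, 20/0/3 | 100% | (20 - 3)/20 = 85% | PASI 75, 90 and 100 | PASI 75 only |
| Group 2c, 20/2/0 | (20 - 2)/20 = 90% | 100% | PASI 75 and 90 | PASI 75, 90 and 100 |

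**3. Whole arms, literal rule, no imputation.** The Overall Safety SAP, Section 4.3, gives 148 subjects randomised to q8w and 149 to q16w. The result is 148/148 = 100% against 149/149 = 100%: difference 0 and Wald variance 0, for all three criteria.

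**4. Literal rule with non-responder imputation.** Of 297 randomised subjects, 273 entered withdrawal and 9 were re-treated without a withdrawal phase (Overall Safety SAP, Sections 4.3 to 4.5). That leaves 297 - 273 - 9 = 15 (5.1%). Assume that all 15 are imputed as non-responders; the documents do not give their split by arm. Difference = (1 - a/149) - (1 - b/148), with a imputed in q16w and b in q8w:

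| a / b | q16w minus q8w (points) |
|---|---|
| 8 / 7 | -0.6 |
| 10 / 5 | -3.3 |
| 15 / 0 | -10.1 |
| 0 / 15 | +10.1 |

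If the 3 subjects re-treated before week 68 are also imputed, 18 are affected and the extreme is about 12 points (18/149 = 12.1%; 18/148 = 12.2%). The difference can therefore be non-zero, but each value in the table comes from who left or missed the visit, and none from a week 68 PASI score.

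**5. What a visit-specific rule could show.** The week 68 rates here are assumed, since the documents give none. With 90% in both arms the difference is 0 (unstratified Wald 90% CI -5.7 to 5.7). With 90% on q8w and 80% on q16w it is -10 (-16.7 to -3.3). The literal rule, before imputation, returns 0 in both cases.

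**The case against.** The strongest reply is that Section 11.3 supplies the thresholds and Section 2.1.2 the visits. Section 11.3 itself refers back to Section 2.1.2 for the endpoints, and the Part 3 SAP drops week 28. This is probably what was intended, and a programmer may well have worked that way. It still asks the reader to ignore a visit written into three definitions, next to entries that carry none. The SAPs governing weeks 20 and 68 are not among the documents, so their silence cannot be assumed either way. Part 3 SAP Section 5.6 tabulates binary PASI endpoints back to week 0, but descriptively and only for subjects who entered Part 3, so it does not settle the randomised comparison.

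A reader might infer that every randomised subject is a responder and that the arm difference is zero by construction. The documents do not support that: under Sections 11.3 and 11.11, subjects who discontinue or miss week 68 count as non-responders, as step 4 of the working shows.

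A reader might also infer that loss of clearance in 2a and 2b, or late clearance in 2c, goes unmeasured. It does not. Absolute PASI 0, ≤1 and <3 at week 68 is a separate major secondary endpoint for 2a, 2b and 2c, and it does not use the 11.3 definitions. Nor are all 525 subjects in 2c affected: that group includes subjects with PASI above 0 only at week 20, and the affected number is not given.

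**Conclusion.** The contradiction stands as an error of wording in a stated endpoint rule. Applied literally at week 68, every correctly randomised subject who is not imputed is a responder on PASI 75, 90 and 100. Any arm difference would then reflect only discontinuation or missing visits: 0 before imputation, -0.6 points for a near-even split of the 15 subjects, and about 10 points either way at the extremes.

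This rests on two assumptions: that the 15 are the imputed subjects, and that imputation by analogy carries over the discontinuation and missing-visit rules but not the PASI ≥3 clause, which is the primary endpoint's own failure criterion. If that clause were carried over too, all three endpoints would merely repeat the primary result.

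The reach is limited. These endpoints are exploratory. It would be wrong to read this as a flaw in the primary week 68 endpoint, its non-inferiority test or the sample size, none of which uses these definitions. Nor do the documents show that any reported result is wrong.

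**What to change.** In the three definitions in Protocol Section 11.3, replace the reference to week 28 with the visit being analysed, measured from week 0, in line with Part 3 SAP Section 5.5.1.1. List the difference in that SAP's Appendix 2. Confirm that the Part 1 and Part 2 SAPs and programs used visit-specific PASI for weeks 20 and 68 and for time to response; if they did not, re-run those tables.

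The wording change is a few words, but Section 17.1 requires a formal amendment for any protocol change. Parts 1 and 2 are already complete according to the Part 3 SAP, so an edit alone cannot alter those analyses. A clarification in the study report would serve if no amendment is otherwise planned. The confirmation is the useful part, and it costs one program check.
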